## 9.7 Interpretation and Conclusion

All tests are two-tailed unless otherwise specified and the overall significant level is set to be 0.05. When the number of hypothesis in a test is increased, the Bonferroni correction would be used to test each of the individual tests at a significance level of  $0.05/m$  ( $m$ = number of tests=5, section 9.3). Statistical significance will be demonstrated if the p-value is less than the significance level of test. Regardless of the outcome declared statistically significant, all results could be stated on the Clinical Study Report (CSR).

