## **7.7 Adjustments for Multiplicity**

For comparison of percentage change in TG of three groups with placebo, 100mg vs. 50 mg, and 150mg vs. 100mg, the post hoc tests will be used to detect which group differ from the rest while statistical significance of ANCOVA or Kruskal-Wallis test. For ANCOVA, the required significance criterion alpha is 0.05 divided by the total number of tests. To correct the multiple testing for primary endpoint, the p-value will be adjusted according to Bonferroni's method to reject the null hypothesis (p-value <0.05/m, m= number of tests). In addition, two independent t-test will also be used for pairwise comparison (p-value=0.05 for all multiple tests). For Kruskal-Wallis test, two independent t-test or Wilcoxon rank-sum test will be used for pairwise comparison (p-value=0.05 for all multiple tests).

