## 9.3 Primary Endpoint Analysis

The primary efficacy endpoint (percentage change of TG) for assessing the superiority of Antroquinonol (50mg, 100mg, 150mg) to placebo is the percentage change in patients with hyperlipidemia by using analysis of covariance (ANCOVA) model using baseline measurement as covariates (model 1). If the differences in baseline characteristics, such as gender, age, weight etc., are observed, for comparing the effectiveness between the treatment groups and placebo, the model will be performed by multiple linear model (model 2) to adjust characteristics.

Model 1:  $Y_{\text{percentage change of TG} (\%)} = \beta_1 + \beta_2 X_{\text{treatment}} + \beta_3 X_{\text{baseline of TG}}$

Model 2:  $Y_{\text{percentage change of TG} (\%)} = \beta_1 + \beta_2 X_{\text{treatment}} + \beta_3 X_{\text{baseline of TG}} + \beta_4 X_{\text{significant characteristic in baseline}}$

If statistical significance of ANCOVA treatment effect is reached ( $p\text{-value} < 0.05$ ), Bonferroni's method, and two independent t-test (section 7.7) will be performed post hoc analysis for pairwise comparison of percentage change in TG (Antroquinonol 50 mg vs. Placebo, Antroquinonol 100 mg vs. Placebo, Antroquinonol 150 mg vs. Placebo, Antroquinonol 100 mg vs. Antroquinonol 50 mg and Antroquinonol 150 mg vs. Antroquinonol 100 mg).

If the normal assumption is violated for percentage change of TG in any treatments, Kruskal-Wallis test will replace ANCOVA. If statistical significance of Kruskal-Wallis test treatment effect is reached ( $p\text{-value} < 0.05$ ), two independent t-test or Wilcoxon rank-sum test will be performed post hoc analysis for pairwise comparison of percentage change in TG (Antroquinonol 50 mg vs. Placebo, Antroquinonol 100 mg vs. Placebo, Antroquinonol 150 mg vs. Placebo, Antroquinonol 100 mg vs. Antroquinonol 50 mg and Antroquinonol 150 mg vs. Antroquinonol 100 mg).

Protocol: GHLIP-2-001

Study Sponsor: Golden Biotechnology Corporation

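### For the five pairwise TG comparisons, Holm's step-down test keeps the same familywise 0.05 as single-step Bonferroni and rejects at least as much: a modest, free gain, provided it is made the one deciding rule

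*SAP*

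**What the plan says.** SAP 9.3 lists five pairwise comparisons of percentage change in TG: each of the three doses against placebo, 100 mg against 50 mg, and 150 mg against 100 mg. They are opened by a gate: "If statistical significance of ANCOVA treatment effect is reached" at 0.05.

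For the adjustment, SAP 7.7 says "the p-value will be adjusted according to Bonferroni's method to reject the null hypothesis", with each p-value held to 0.05/m. SAP 9.7 repeats that "the Bonferroni correction would be used to test each of the individual tests at a significance level of" 0.05/m and fixes m as "number of tests=5, section 9.3". The overall level comes from the same section: "All tests are two-tailed unless otherwise specified and the overall significant level is set to be 0.05". No step-down method is named in either document. The protocol (Protocol Summary and 9.4) also specifies ANOVA with a Bonferroni adjustment.

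The plan has more to its rule than that. After a significant ANCOVA, SAP 9.3 says "Bonferroni's method, and two independent t-test (section 7.7) will be performed post hoc analysis for pairwise comparison of percentage change in TG". SAP 7.7 explains the second of these: "In addition, two independent t-test will also be used for pairwise comparison (p-value=0.05 for all multiple tests"). If normality fails, Bonferroni drops out: "For Kruskal-Wallis test, two independent t-test or Wilcoxon rank-sum test will be used for pairwise comparison (p-value=0.05 for all multiple tests"). The SAP does not say which pairwise result decides.

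**The concern.** Single-step Bonferroni holds every comparison to 0.01 whatever the other four show. Holm orders the p-values and relaxes the threshold after each rejection. It needs no further assumption about how the tests are correlated, and it cannot lose a rejection that Bonferroni makes. What Bonferroni offers in return is simple matching simultaneous confidence intervals. The SAP plans none for pairwise TG differences; the intervals in SAP 7.12, 8 and 10.2 are descriptive.

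At stake is the ability of a four-arm trial to say which doses beat placebo, beyond the first one found. Power is thin to begin with, because Protocol 9.2 and SAP section 5 size the trial for one comparison at one-sided 0.025, with no allowance for five tests.

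**Working it through.** **The plan's own threshold.** 0.05/5 = 0.01 per test. This reproduces.

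**Holm's thresholds on the same five ordered p-values.** 0.05/5 = 0.01, 0.05/4 = 0.0125, 0.05/3 = 0.0167, 0.05/2 = 0.025 and 0.05/1 = 0.05, stopping at the first failure. The first step equals Bonferroni's, so the chance of rejecting at least one of the five is identical by construction. Any gain can come only from later steps.

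**Inputs.** 24 evaluable per group, a reduction of 27.5 points and SD 40 (Protocol 9.2); five comparisons and the global gate at 0.05 (SAP 9.3); overall two-sided 0.05 (SAP 9.7). SAP section 5 instead quotes SDs of 2.4 and 5.3. On those, about 1 patient per group would suffice and the choice of procedure would hardly matter. SD 40 is used because the protocol states it alongside 27.5.

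**Starting power for one comparison (normal approximation).** Standard error = 40 × √(2/24) = 11.55, and 27.5/11.55 = 2.38.
- At two-sided 0.05: Φ(2.38 − 1.96) = Φ(0.42) ≈ 0.66.
- At two-sided 0.01: Φ(2.38 − 2.576) = Φ(−0.19) ≈ 0.42.

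**Bonferroni against Holm.** Simulation of 100,000 trials per scenario: normal data, pooled-variance t-tests, global F test at 0.05 as gate, no baseline covariate, Monte Carlo standard error at most 0.002. The effect patterns are assumptions. The linear pattern is 27.5 × 1/3, 2/3 and 1. The third pattern uses the literature difference quoted in Protocol 9.2, 36.6 + 0.7 = 37.3.

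| Assumed effect (50/100/150 mg) | Quantity | Bonferroni | Holm |
|---|---|---|---|
| 27.5 / 27.5 / 27.5 | power per dose | 0.40 | 0.43 |
| | all three doses declared | 0.18 | 0.23 |
| | at least one dose declared | 0.635 | 0.635 |
| 9.2 / 18.3 / 27.5 | 50 mg | 0.036 | 0.046 |
| | 100 mg | 0.152 | 0.168 |
| | 150 mg | 0.391 | 0.398 |
| 37.3 / 37.3 / 37.3 | power per dose | 0.72 | 0.76 |
| | all three doses declared | 0.51 | 0.59 |
| | at least one dose declared | 0.905 | 0.905 |

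The linear-case gains are 0.010, 0.016 and 0.007. Holm rejected more hypotheses than Bonferroni in about 4% to 12% of trials in which some dose worked, and never fewer.

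**Sensitivity.** With each pair's own variance in place of the four-arm pooled variance, and 27.5 for all doses, power per dose goes from 0.38 to 0.41 and all three from 0.16 to 0.22. The levels are about 2 points lower and the gain is similar.

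**Error control.** Familywise error with Holm was at most 0.036 in every scenario with the gate and at most 0.042 without it. The unadjusted 0.05 tests that the SAP also allows gave, with the gate, 0.048 when no dose works, but 0.085 to 0.112 when some doses work and other comparisons are truly null.

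**The case against.** The strongest reply is that Bonferroni is a valid, prespecified and conservative method, so nothing is in error, and that 3 points per dose is small beside a starting power of about 0.42. Both parts stand. A reader might infer that the SAP's choice is a mistake, or that Holm would rescue the trial's power. The documents and the arithmetic support neither.

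The primary objective (Protocol 2.1, SAP 3.1.1) is TG reduction against placebo, and the formal hypothesis in SAP 9.1 is global. Neither requires all three doses to be declared. This limits the weight of the all-three figure. It does not remove the interest in dose-by-dose results, since SAP 9.3 lists those comparisons itself.

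A larger gain is tempting. If only the three placebo comparisons were counted, power per dose would go from 0.46 to 0.53 with the gate, and without the gate the chance of declaring all three doses from about 0.24 to 0.39. SAP 9.7 fixes the family at five, so those figures describe a different plan.

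A reader might also take an equal effect at all three doses as the planned scenario. Protocol 9.2 gives one assumed reduction and no dose-response shape. The equal-effect case is an assumption, and a favourable one for Holm.

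Finally, power is not simply given up, because the SAP also runs the same TG comparisons at unadjusted 0.05, and on the Kruskal-Wallis route applies no Bonferroni at all. This objection stands in full. Putting Holm into 9.7 alone would leave error control undefined.

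**Conclusion.** The point holds as an efficiency improvement, not as an error. With the SAP's five comparisons, single-step Bonferroni can be replaced by Holm at the same familywise 0.05 with no rejection lost. If all three doses reduce TG by 27.5 points, the gain is about 3 points of power per dose and about 5 points in the chance of declaring all three. Under a linear dose response it is about 1 point per dose (0.7 to 1.6). The chance of finding at least one difference is unchanged.

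These sizes rest on 24 per arm, a common SD of 40, normal data and no gain from the baseline covariate. The ordering of the two procedures rests on none of these. The claim of familywise control applies to the trial's TG conclusions only if the unadjusted pairwise tests lose their deciding role.

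**What to change.** In SAP 7.7, 9.3 and 9.7, use one rule on both routes: *After a significant global test, the five pairwise TG p-values (from the ANCOVA contrasts or, on the Kruskal-Wallis route, from Wilcoxon rank-sum tests) are tested by Holm's procedure at overall two-sided 0.05. Holm-adjusted p-values are reported, and this rule decides which pairwise differences are declared.*

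Delete the parallel unadjusted 0.05 TG tests in 7.7 and 9.3, or label them exploratory. Section 12 now declares no statistical change from the protocol; record there the move from the protocol's Bonferroni adjustment to Holm.

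The cost is a few sentences in three SAP sections and one entry in section 12. It needs no patients, no data and no loss of error control. Simple Bonferroni-type simultaneous intervals would no longer match the tests, but none are planned. The change must be made before database lock and unblinding, both of which SAP 6.2 makes conditional on an approved SAP.

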# 10 SAFETY ANALYSES

The analysis of safety assessments in this study will include summaries of the following categories of safety and tolerability data collected for each subject:

- Adverse Events
  - AEs and SAEs
  - AEs leading to withdrawal
  - Any Deaths

**Protocol: GHLIP-2-001**

**Study Sponsor: Golden Biotechnology Corporation**

- Clinical Laboratory Investigations
- Other Safety measures: vital signs, ECG, physical examinations

Safety assessments consist of monitoring and recording all adverse events, laboratory tests, vital signs and physical examinations. Adverse event incidence rates in each group will be summarized by system organ class and preferred terms. Each subject will be counted only once within a system organ class or a preferred term and any repetitions will be ignored.

## **10.1 Adverse Events**

Adverse events will be coded using the Medical Dictionary for Regulatory Activities (MedDRA) central coding dictionary Version 20.0.

### **10.1.1 All Adverse Events**

Summaries of incidence rates (frequencies and percentages), intensity, and relationship to study drug of individual AEs by System Organ Class and Preferred Term (MedDRA) will be prepared. Each patient will be counted only once within each preferred term per study period. If a patient experiences more than one AE within a prepared item for the same recording period, only the AE with the strongest relationship or the greatest intensity, as appropriate, will be included in the summaries of relationship and intensity.

Summaries will be presented by treatment group for Antroquinonol. Fisher's exact test will be used to compare rates for System Organ Classes across treatment groups. A similar summary by treatment group will be presented for all patients in the Safety Population.

Counts of AEs by maximum intensity will be presented for patients in the Safety Population by treatment group, grouped by the treatment the patient had received most recently prior to the

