- AEs, laboratory parameters, and vital signs will be reported descriptively, based on the safety population (all randomized patients who received at least one dose or partial dose of study treatment). Safety will also be assessed by a review of all safety endpoints including adverse events (AEs), laboratory examinations, and electrocardiogram test.

Unless otherwise specified, all statistical assessments will be two-sided under significant level of 0.05.

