8.2. Expected Adverse Reactions

In clinical trials, observed adverse effects of Antroquinonol are summarized as following:

- Diarrhea (92.31%)
- Vomiting (69.23 %)
- Nausea (53.85 %)

If a GI event occurs, adequate drugs/therapies could be administered based on investigator's judgements. If the event is judged as grade 3 according to CTCAE v4.03, this event will be seen as a serious adverse event.

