9.2. Sample Size Considerations

The primary efficacy endpoint in this trial is “to compare the percentage change of triglyceride (TG) from baseline following a 12-week regimen of Antroquinonol versus placebo.” The objective of this trial is to assess the efficacy of the study treatment compared with control treatment. According to the literature review (FDA statistical reviews of Fibrate), the TG reduction percentage change of Fibrate from baseline to last visit was 36.6% for subjects who were treated with the study treatment, and 0.7% increased for the control treatment. According to prior published clinical reference, it is assumed that the mean TG percentage reduction is 27.5% and standard deviation is 40. The evaluable patient number should be at least 24 patients for each group under one-sided significance level 0.025 and power 90%. Considering a 20% drop-out rate, a sample size of 30 patients should be enrolled to each group, and a total of 120 patients will be recruited into this study. The sample size calculation was derived using PASS 2008.

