## **4 STUDY METHOD**

### **4.1 Overall Study Design and Plan**

The study design is constructed as a multi-center, prospective, double-blind, randomized, placebo-controlled study to assess the reduction of TG by Antroquinonol, in comparison with placebo, after 12 weeks of treatment in patients aged between 20 and 75 years with hypercholesterolemia and hyperlipidemia. Enrolled patients are randomized in 1: 1: 1: 1 ratio to Antroquinonol 150 mg, Antroquinonol 100 mg, Antroquinonol 50 mg, or placebo.

Protocol: GHLIP-2-001

Study Sponsor: Golden Biotechnology Corporation

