### **9.2 Test of Assumptions**

The continuous variables will be compared using Student's t test (2 groups) or analysis of variance ( $> 2$  groups). If the conditions for applying these tests are not met normality assumption, the Wilcoxon rank sum (2 groups) or Kruskal-Wallis ( $> 2$  groups) non-parametric tests will be used. Comparison within group will be tested by using paired t test. If the normal assumption is violated, the Wilcoxon signed-rank test will be conducted. The category variables will be compared between groups using the Chi-square test if the theoretical total of each class studied is greater than 5. Otherwise Fisher's exact test will be used.

Protocol: GHLIP-2-001

Study Sponsor: Golden Biotechnology Corporation

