### **10.1.2 Adverse Events Leading to Withdrawal**

A summary of incidence rates (frequencies and percentages) of AEs leading to withdrawal, by treatment group, System Organ Class, and Preferred Terms, will be prepared for the Safety Population. No statistical tests will be performed.

A data listing of AEs leading to withdrawal will also be provided, displaying details of the event(s) captured on the CRF.

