### 10.1.5 Other AE Assessments

No other assessments or analysis are planned.

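### Adverse event rates across four ordered doses get only an unordered Fisher test by organ class; a prespecified trend test beside it would be a cheap gain for moderate dose gradients

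*SAP*

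**What the plan says.** Four equally spaced doses, counting placebo as 0 mg, are allocated equally: "Enrolled patients are randomized in 1: 1: 1: 1 ratio to Antroquinonol 150 mg, Antroquinonol 100 mg, Antroquinonol 50 mg, or placebo" (SAP 4.1). Protocol 9.2 sets the arm size: "a sample size of 30 patients should be enrolled to each group". The safety population is everyone who took at least one dose (SAP 7.4.3), so about 30 per arm.

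For AE rates, SAP 10.1.1 plans that Fisher's "exact test will be used to compare rates for System Organ Classes across treatment groups". The other AE sections add no test:

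- AEs leading to withdrawal (SAP 10.1.2): "No statistical tests will be performed". SAP 10.1.3 repeats this for serious AEs.
- Other AE assessments (SAP 10.1.5): "No other assessments or analysis are planned".
- The general rule for categorical data (SAP 9.2) is also unordered: "The category variables will be compared between groups using the Chi-square test if the theoretical total of each class studied is greater than 5", and Fisher's test otherwise.

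The statistical part of the protocol summary treats safety as descriptive: "AEs, laboratory parameters, and vital signs will be reported descriptively, based on the safety population". SAP 10 and 10.1.1 tabulate incidence by arm for organ classes and for preferred terms. Protocol 8.2 lists three expected reactions with rates from earlier trials: diarrhea 92.31%, vomiting 69.23% and nausea 53.85%. It gives no breakdown by dose and no placebo rate.

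**The concern.** A four-arm Fisher test spreads its sensitivity over every way in which four rates can differ. If toxicity rises steadily with dose, a test that uses the order concentrates on that pattern and detects it more often from the same data. The SAP does look at dose steps for efficacy: SAP 9.3 compares 100 with 50 mg and 150 with 100 mg. It has no counterpart for AEs.

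The test is also run only on organ classes. The three reactions that Protocol 8.2 singles out are preferred terms, and within a class they are pooled with other events. The documents do not allow that dilution to be quantified.

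What is at stake is interpretation. A non-significant Fisher p-value printed beside a rising pattern could be read as reassurance. A trend test added after unblinding would have to be labelled unplanned (SAP 2 and 6.2).

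**Working it through.** **Plan's own figure.** There is none to reproduce. Neither document states power or an expected rate by dose for AEs. All rates below are assumptions.

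**Inputs from the documents.** Four arms, 1:1:1:1, 30 per arm, two-sided 0.05 (SAP 7.12).

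**Hand check of the mechanism.** Assume 10/20/30/40%, so expected counts are 3, 6, 9 and 12 of 30. The total is 30 of 120 and the pooled rate is 0.25.

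- Unordered chi-square on 3 df: Σ(x − 7.5)² / (30 × 0.25 × 0.75) = (20.25 + 2.25 + 2.25 + 20.25) / 5.625 = 8.0.
- Trend with scores 0, 1, 2, 3 (equivalent to 0, 50, 100, 150): T = 6 + 18 + 36 = 60; expected 1.5 × 30 = 45; variance 0.25 × 0.75 × (420 − 180²/120) = 0.1875 × 150 = 28.125. Then (60 − 45)² / 28.125 = 8.0 on 1 df.

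The signal is the same 8.0, but the unordered test needs 7.81 (3 df) and the trend test 3.84 (1 df). With non-centrality 8.0, approximate power is 65% against 81%.

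For a plateau at 10/40/40/40% (counts 3, 12, 12, 12) the same formulas give 9.2 in total, of which only 5.5 is trend. There the ordered test is weaker.

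**Exact calculation.** For 30 per arm, all 31⁴ outcomes were enumerated.

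- Fisher-Freeman-Halton: given total s, a table has probability ΠC(30, xᵢ) / C(120, s); p is the sum over tables no more probable than the observed one.
- Exact Cochran-Armitage: p is the conditional probability that |T − 1.5s| is at least as large as observed.
- Power is the binomial probability of all outcomes with p ≤ 0.05.

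| Assumed rates, 0/50/100/150 mg (%) | Fisher | Exact trend | Gain (points) |
|---|---|---|---|
| 10/15/20/25 | 22.7 | 31.9 | 9.3 |
| 5/15/25/35 | 77.4 | 87.2 | 9.8 |
| 5/10/15/20 | 29.3 | 41.1 | 11.8 |
| 10/20/30/40 | 67.2 | 80.3 | 13.1 |
| 5/10/20/30 | 66.5 | 80.1 | 13.6 |
| 10/15/25/35 | 55.0 | 69.9 | 14.9 |
| 20/30/40/50 | 56.5 | 71.5 | 15.0 |
| 20/35/50/65 (steeper) | 91.1 | 96.7 | 5.6 |
| 10/25/40/55 (steeper) | 95.0 | 98.3 | 3.3 |
| 20/40/60/80 (steep) | 99.7 | 99.9 | 0.3 |
| 10/10/40/40 (step at 100 mg) | 92.4 | 93.0 | 0.6 |
| 10/10/10/40 (top dose only) | 83.6 | 79.9 | −3.7 |
| 10/40/40/40 (plateau) | 81.7 | 64.3 | −17.4 |
| 10/10/40/10 (not monotone) | 83.6 | 8.5 | −75.2 |

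Gains were taken before rounding, so some differ by 0.1 from the difference of the printed powers.

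**At the rates in Protocol 8.2.** Suppose, as an assumption, that those rates apply at 150 mg and rise roughly linearly from a low placebo rate. Diarrhea at 10/37/65/92% and vomiting at 5/26/48/69% give about 100% for both tests. Nausea at 5/21/38/54% gives about 99% for Fisher and 99.7% for the trend test.

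**False positives.** With all rates at 10%, Fisher rejects in 4.1% of trials and the exact trend test in 3.6%. At least one of them rejects in about 6%, for each class or term tested.

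**The case against.** The strongest case against is that the dose-response for toxicity is unknown, so a test that assumes no shape is a defensible choice for safety. The table supports this: a trend test used alone would do worse for a plateau or a top-dose-only effect and would nearly miss a non-monotone one. That stands, and it rules out replacing Fisher. It does not argue against reporting both.

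Second, AE reporting is mainly descriptive. Diarrhea, vomiting and nausea will be tabulated by arm, so a gradient would be visible without a p-value, and the documents tie no safety decision or stopping rule to this test. That also stands, and it keeps the severity low.

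Three stronger readings are tempting, and the documents do not support them:

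- **A fixed loss of 15 to 18 points.** A reader might take this from a large-sample trend test under a few moderate gradients. The documents supply no rates by dose, the exact test gains less (13.1 rather than 15.8 points at 10/20/30/40%), and other shapes give zero or negative gains.
- **Tolerability by dose as a stated objective.** Protocol 2.2 item 4 asks for safety and tolerability compared with placebo. The interest in dose order is inferred from the design.
- **The planned test would miss the named reactions.** At rates like those in Protocol 8.2 it would miss almost nothing. Those rates come from earlier trials and may not carry over, but they are the only ones given.

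Finally, SAP 10.1.1 says only that the test runs across treatment groups, just after a sentence about summaries for Antroquinonol. Four arms is the natural reading, but it is not spelled out.

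**Conclusion.** The point holds as a low-severity improvement. The only between-arm test of AE rates named in the AE sections ignores dose order and stops at organ class, and no dose-trend test is planned in either document. Under assumed moderate, steadily rising rates at 30 per arm, an exact trend test would add roughly 9 to 15 points of power. With 24 per arm the 10/20/30/40% case is similar (55.7% against 70.0%). The gain depends wholly on the assumed shape and level of the rates, and it vanishes or reverses as the table shows. The planned Fisher test is not wrong. It is incomplete for a dose-ranging design.

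**What to change.** In SAP 10.1.1, before unblinding:

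1. Keep the Fisher test and state that it compares all four arms, placebo included, if that is what is meant.
2. Add a two-sided exact Cochran-Armitage trend test with scores 0, 50, 100 and 150, for organ classes and for diarrhea, vomiting and nausea as preferred terms.
3. Label these tests exploratory and uncorrected, and report both p-values beside the by-arm incidence tables whatever their result.
4. Align SAP 10.1.5 with the addition.

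The cost is a few lines of SAS and no new data. The downside is a few more uncorrected safety p-values, with about a 6% chance per class or term that either test is significant at a common rate of 10%. The trend test is weak for plateau or non-monotone patterns, which is why it is added and not substituted.
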